8.3. Injection Site Reactions

Summaries of ISR data (including nature, timing and whether or not the ISR was Grade 1 or higher) will be provided by treatment group and overall, and the differences in proportions of subjects experiencing ISRs between groups will be compared in Part 2 using Fisher's exact tests.

8.4. Delayed Return to Ovulation

The probability of return to ovulation more than 12 months after treatment initiation will be estimated using Kaplan-Meier methods and presented with 95% CIs, by treatment group.

8.5. Menstrual Bleeding Disturbances

The percentage of women experiencing amenorrhea or other menstrual bleeding disturbances (irregular bleeding or spotting) assessed monthly and at day 7, week 13, week 32, and the final study visit will be compared between treatment groups using frequency tables (for monthly data, the bleeding history report obtained closest in time to the target monthly visit - among visits within 14 days of the target - will be used). The number and percentage of subjects ever reporting spotting, irregular bleeding, or unacceptable bleeding pattern will also be tabulated.

For Part 2 only, weekly diary data were divided into 30-day segments starting from the date of the injection. For each 30-day period, subjects were categorized into one of the following four types:

- No bleeding or spotting: no bleeding or spotting days recorded during the entire 30-day period.
- Spotting only: only days with spotting recorded during the 30-day period
- 3. Bleeding only: only days with bleeding recorded during the 30-day period

 Bleeding and spotting: a mixture of bleeding and spotting days recorded during the 30day period.

The percentage of subjects experiencing each of the four bleeding patterns during months 1, 3, 6, 9, and 12 will be compared between treatment groups using frequency tables.

8.6. Liver Function Tests

For Part 2 only, liver function tests, including but not limited to ALT and AST, will be assessed by tabulating and graphing change from baseline to week 13 (month 3), week 32 (month 7.5), and final study visit data.

8.7. **Mood**

For Part 2 only, mood will be assessed in frequency tables at baseline and at week 13 (month 3), week 32 (month 7.5), and final study visits.

8.8. Vital Signs and Body Weight

Pulse rate, systolic/diastolic blood pressure, body weight and BMI will be summarized in listings and tabulated descriptive statistics by center, treatment group and study visit. Vital signs will also be summarized graphically and using shift-tables (mean and median change from baseline to day 7, month 3, and month 7.5), by center and treatment group.

8.9. Concomitant Medications or Therapies

Concomitant medications include medications that started at any time and were taken at any time during the study, up to the end of study as defined in the study protocol. The use of concomitant medications will be summarized by therapeutic class and category (coded using Lexicomp and PDR Online) with descriptive statistics. Subjects are counted only once in each therapeutic class, and only once in each preferred term category.

9. ACCEPTABILITY DATA ANALYSIS

Acceptability analyses will be performed on the Treated Population and summarized using descriptive statistics and data listings. Responses to acceptability questions regarding menstrual patterns will be assessed at monthly and final study visits, and compared between treatment groups at month 7.5 using Fisher's exact tests. Perceptions of pain at time of injection and responses on other acceptability questionnaire items, as well as assessment of ease of injection by the study staff, will likewise be summarized.

10. PHARMACOKINETICS ANALYSIS

For both Part 1 and Part 2, individual MPA profiles will be displayed (both in the original scale and using semi-log plots) through month 12 following treatment initiation or earlier date of withdrawal from the study using the Primary Evaluable Analysis Set, with post-baseline MPA concentrations that fall below the limit of quantification (LOQ) replaced by half the applicable LOQ. If 120 mg/mL is selected as one of the Part 2 dose groups, then subjects in that Part 1 group will be incorporated in the primary Part 2 pharmacokinetics analysis. Data from the subset of 6 subjects (2 per dose group) with extreme obesity (BMI ≥40) in Part 2, and subjects with detectable MPA at baseline or who used drugs known to interfere with pharmacokinetics or pharmacodynamics of MPA prior to return to ovulation, will be excluded from the primary analysis but will be described separately. Sparse data collected after month 12 will likewise be described separately for the subset of subjects who have not ovulated by month 12.

The following non-exhaustive list of pharmacokinetic parameters and metrics will be estimated based on non-compartmental analysis implemented using Phoenix WinNonlin® or a validated SAS® macro (Matos-Pita 2005): C_{max}, t_{max}, C₉₁, C₁₈₂, C₂₁₀, AUC₀₋₉₁, AUC₉₁₋₁₈₂, AUC₀₋₁₈₂, AUC₀

Summaries of pharmacokinetic parameter estimates in each treatment group will include means, medians, GMs, minima, maxima, SD, %CV, and 95% CIs for GMs. The number and percentage of participants with C₁, C₉₁, C₁₈₂ and C₂₁₀ below 0.1 ng/mL and 0.2 ng/mL, and the time above 0.1 ng/mL, will be summarized by group. The predicted drug accumulation after repeat dosing will be based on observed mean drug concentrations at months 6 and 12 (when routine PK testing ends). Steady state concontrations will be predicted using an appropriate PK model for drug concentrations at months 18, 24, etc., following each successive hypothetical dose given at 6-month intervals.

The pharmacokinetics of MPA will be compared between groups based on 90% CIs for GM ratios of C_{max}, C₁₈₂, C₂₁₀, AUC₀₋₁₈₂, AUC₀₋₂₁₀, AUC_{0-∞}, and apparent half-life. The effects of dose group, investigational center, BMI, and age on C_{max}, C₁₈₂, AUC₀₋₁₈₂, and half-life in Part 2 will be explored graphically and using analysis of covariance on log-transformed outcomes. Dose proportionality of C_{max}, C₁₈₂, AUC₀₋₁₈₂, and half-life will be explored based on dose-normalized pharmacokinetic estimates. Sensitivity analyses will be performed after excluding participants determined to be outliers (eg, due to strong suspicion of injection on or near a blood vessel) or who fail to complete 7.5 months of follow-up.

In addition to non-compartmental analyses, nonlinear mixed effect pharmacokinetics modeling will be performed to estimate rates of absorption, relative bioavailability and other relevant pharmacokinetic parameters. Modeling and simulation will also be performed to assess the contraceptive potential of a dose other than that tested in Part 1 or Part 2, incorporating historical data as available and appropriate. Details of the methods used for modeling and simulation exercises will be described in a separate Modeling and Simulation Plan.

11. PHARMACODYNAMICS ANALYSIS

11.1. General

The Primary Evaluable Set will be used for the assessment of pharmacodynamics endpoints for both Part 1 and Part 2 data.

11.2. Primary Pharmacodynamics Endpoints and Analysis

The primary pharmacodynamics endpoint is time to ovulation, defined as a single elevated serum $P \ge 4.7$ ng/mL. Time to ovulation will be computed as the difference in days between detection of the first post-randomization elevated P and the date of treatment initiation. Because measurement of P will only occur at weeks 61-65 and 75-78 for women who have not ovulated by month 12, participants who do not experience the endpoint on or before their month 12 visits will have their event times censored at month 12 for purposes of the primary analysis. However, these data may be included in secondary analyses that account for the interval-censored nature of endpoints observed after month 12. Although women with $P \ge 4.7$ ng/mL are asked to return within 5 days, confirmation of an elevated P is not a component of the primary endpoint definition. The potential for incorrect timing of endpoints (eg, if a participant missed one or more visits prior to first elevated P) will be described on a case-by-case basis when interpreting the study findings or through sensitivity analyses.

If 120 mg is selected as one of the doses in Part 2, then subjects assigned to that group in Part 1 will be incorporated in the analysis of Part 2 data. Cumulative probabilities of return to ovulation will be estimated for each treatment group based on the Kaplan Meier method, with 95% CIs derived using the complementary log-log transformation.

Differences in the distribution of return to ovulation between groups will be explored based on two-sided log-rank tests conducted at the 0.05 significance level, stratified on investigational center. For descriptive purposes the median, inter-quartile range, minimum, and maximum time to ovulation will be reported by treatment group.

Any outcomes excluded from the Primary Evaluable Analysis Set, and the reason(s) for exclusion (eg, use of excluded medications), will be described separately. Data from the subset of 6 subjects (2 per treatment group) with extreme obesity (BMI \geq 40) will likewise be described separately. If more than 10% of women go more than two weeks (14 days) between their last P < 4.7 ng/mL visit and their first P \geq 4.7 ng/mL visit, then sensitivity analyses will be performed to estimate and compare cumulative probabilities of return to ovulation using Turnbull's extension of the Kaplan-Meier estimator for interval censored data (Turnbull 1976).

Individual P and estradiol (E2) concentration data will be displayed graphically from the pretreatment period through time of ovulation. Mean and maximum E2 concentrations in each 30day follow-up period will be summarized across subjects using means, medians, and SD.

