# **AMENDMENT HISTORY**

The protocol for Study TV46046-WH-10075 (original protocol dated 01 May 2016) has been amended and reissued as follows:

Amendment 01	29 May 2016 No subjects have been enrolled to date.
Amendment 02	04 November 2016 No subjects have been enrolled to date.
Amendment 03	27 March 2017 6 subjects have been enrolled to date
Amendment 04	09 August 2017 12 subjects have been enrolled to date

Details about the changes and reason/justification for each change are provided in Section 16.

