- a For subjects in whom ovulation returns before month 12 post-injection, the final study visit will be scheduled at month 12. If ovulation occurs between months 12 and 18 (between weeks 52 and 78), at the time when the defining serum progesterone result becomes available, the study staff will inform the subject that she needs to return within 5 days to the investigational center for the final study visit. For subjects in whom ovulation does not return by month 18, the laboratory visit at week 78 will be considered the final study visit
- b A urine pregnancy test will be performed at enrollment; and during the study, if indicated.
- c Day 0; within the 1st 5 days of the start of subject's menstrual cycle.
- d Blood samples for serum progesterone and estradiol will be collected approximately twice weekly during the approximately 2 to 3 weeks preceding the subject's expected menses for confirmation of ovulation (ideally at least 4 measurements).
- e Blood samples for serum progesterone and estradiol will be collected on day 0 (baseline); then at day 7 and then weekly through week 32, regardless of ovulation status. If ovulation does not return by week 32, then weekly blood samples for serum progesterone and estradiol will continue to be collected until ovulation or through week 52, whichever is earlier. If there is no ovulation by week 52, then blood samples for progesterone and estradiol will be collected at weeks 61, 62, 63, 64, and 65; and at weeks 74, 75, 76, 77, and 78, if ovulation has not returned by week 65. During these additional laboratory visits, blood samples will be collected and tested for serum progesterone and estradiol at all visits, but not past return to ovulation.
- f At any time during follow-up, subjects with initial serum progesterone ≥3.0 ng/mL will be asked to return within 5 days for repeated progesterone and estradiol measurement. If repeated progesterone is at 3 ng/mL or below, the subject will continue follow-up per their visit schedule.
- g At any time during follow-up, if the serum progesterone level is ≥4.7 ng/mL, subjects will be asked to return within 5 days for repeated progesterone and estradiol measurement.

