
 
d At any time during the study, subjects with initial serum progesterone ≥3.0 ng/mL will be asked to return within 5 days for repeated progesterone measurement. If repeated progesterone is at 3 ng/mL or below, the subject will continue follow up per their visit schedule.
 
e In addition, at any time during the study, if the serum progesterone level is equal to or greater than 4.7 ng/mL, subjects in all treatment groups will be asked to return to repeat the serum progesterone measurement within 5 days.
 
f d During pretreatment, bBlood
 
	d Blood samples for serum progesterone and estradiol will be collected approximately twice weekly during the approximately 2 to 3 weeks preceding the subject's expected menses for confirmation of ovulation (ideally at least 4 measurements).	Clarification
samples for serum progesterone and estradiol will be collected approximately twice weekly during the approximately 2 to 3 weeks preceding the subject's expected menses for confirmation of ovulation (ideally at least 4 measurements).		

Original text with changes shown	New wording	Reason/Justification for change

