f At any time during follow-up, subjects with initial serum progesterone ≥3.0 ng/mL will be asked to return within 5 days for repeated progesterone and estradiol measurement. If repeated progesterone is at 3 ng/mL or below, the subject will continue follow-up per their visit schedule.	f At any time during follow-up, subjects with initial serum progesterone ≥3.0 ng/mL will be asked to return within 5 days for repeated progesterone and estradiol measurement. If repeated progesterone is at 3 ng/mL or below, the subject will continue follow-up per their visit schedule.	Addition. Details included to describe the follow-up process for subjects with initial serum progesterone greater than 3.0 ng/mL.

Original text with changes shown	New wording	Reason/Justification for change
g At any time during follow-up, if the serum progesterone level is ≥4.7 ng/mL, subjects will be asked to return within 5 days for repeated progesterone and estradiol measurement within 5 days. and serum MPA at (weeks 61 and 74). Estradiol will be measured at all of the same time points as progesterone as a supporting pharmacodynamics measure.h If the estradiol level is at or greater than 75 pg/mL during weeks 2 to 12 or weeks 52 to 78, then blood samples for progesterone and estradiol will be collected weekly.	g At any time during follow-up, if the serum progesterone level is ≥4.7 ng/mL, subjects will be asked to return within 5 days for repeated progesterone and estradiol measurement.	Clarification.
h i During the follow up visits, b B lood samples for MPA will be collected on day 0; then on at days 1, 2, 3, 5, 7, 10, 12, 14, 18, 2 01 , 28, 35, and 42; then at weeks 8, 10, 12, 13, 15, 17, 19, 21, 23, 25, 26, 28, 30, and 32; and then every 28 days until week 52 , regardless of ovulation status .	h Blood samples for MPA will be collected on day 0; then on days 1, 2, 3, 5, 7, 10, 12, 14, 18, 21, 28, 35, and 42; then at weeks 8, 10, 12, 13, 15, 17, 19, 21, 23, 25, 26, 28, 30, and 32; and then every 28 days until week 52, regardless of ovulation status.	Clarification.

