Estradiol, an additional pharmacodynamic indicator, will be measured every time progesterone is measured. It will be used to more accurately characterize ovarian function. Before the time period when progesterone is measured weekly, subjects in any group who have an estradiol result of 75 pg/mL or higher (ie, during weeks 2 to 12 or weeks 52 to 78) will be asked to return for weekly progesterone and estradiol testing.	Estradiol, an additional pharmacodynamic indicator, will be measured every time progesterone is measured. It will be used to more accurately characterize ovarian function.	Correction.
Section 7. Assessment Of Safety	Γ	1
In this study, safety will be assessed by qualified study personnel by evaluating the following: vital signs (BP [systolic/diastolic], pulse, and respiration), body weight, adverse events, concomitant medication usage, changes in menstrual bleeding patterns, mood, liver function tests, occurrence of ISRs, and return to ovulation after 12 months after the study drug injection.	In this study, safety will be assessed by qualified study personnel by evaluating the following: vital signs (BP [systolic/diastolic], pulse, and respiration), body weight, adverse events, concomitant medication usage, changes in menstrual bleeding patterns, mood, liver function tests, occurrence of ISRs, and return to ovulation after 12 months after the study drug injection.	Clarification.
Section 7.8.Menstrual Bleeding Patterns		
Study subjects will be asked about changes in their menstrual bleeding patterns, including no bleeding, since last assessment, at monthly intervals (in Part 1 only) and during the scheduled follow-up visits in both Part 1 and Part 2 at week 13 (month 3) and week 32 (month 7.5), and at the final study visit.	Study subjects will be asked about changes in their menstrual bleeding patterns, including no bleeding since last assessment, at monthly intervals (in Part 1 only) and during the scheduled follow-up visits in both Part 1 and Part 2 at week 13 (month 3) and week 32 (month 7.5), and at the final study visit.	Clarification.

Original text with changes shown	New wording	Reason/Justification for change
Section 7.12. Assessment Of Accepta	ability	

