Blood samples for MPA will be collected and stored for possible future MPA testing (if necessary) any time when samples are collected for serum progesterone and estradiol up until Month 12, except for pre-treatment visits and visits for confirmation of ovulation.	Blood samples for MPA will be collected and stored for possible future MPA testing (if necessary) any time when samples are collected for serum progesterone and estradiol up until Month 12, except for pre-treatment visits and visits for confirmation of ovulation.	Text moved to month 12 section.
Section 3.14.3.2.3. Laboratory Visits	after Week 52	
During these additional laboratory visits, blood samples will be collected and tested for serum progesterone and estradiol (all visits) and serum MPA (weeks 615 and 748).Blood samples for MPA will be collected and stored for possible future MPA testing (if necessary) any time when samples are collected for serum progesterone and estradiol.	During these additional laboratory visits, blood samples will be collected and tested for serum progesterone and estradiol (all visits) and serum MPA (weeks 61 and 74).	Text revised to replicate collection times in similar studies.
Table 1:         Study Procedures and Ass	essments (Parts 1 and 2)	
Mammogram n	Mammogram n	Added
g. During the follow-up laboratory visits, blood samples for serum progesterone and estradiol will be collected at weeks 1, 2, 4, 6, 8, 10, and 12; then weekly through week <del>32</del> 52 . If ovulation does not return by week <del>32</del> , then weekly blood samples for serum progesterone and estradiol will continue to be collected until ovulation or through week 52 , whichever is earlier.	g. During the follow-up laboratory visits, blood samples for serum progesterone and estradiol will be collected at weeks 1, 2, 4, 6, 8, 10, and 12; then weekly through week 52.	Correction. Text revised to replicate collection times in similar studies.
g. During these additional laboratory visits, blood samples will be collected and tested for serum progesterone and estradiol (all visits) and serum MPA	g. During these additional laboratory visits, blood samples will be collected and tested for serum progesterone and estradiol (all visits) and serum MPA	Correction. Text revised to replicate collection times in similar studies.

Original text with changes shown	New wording	Reason/Justification for change	
(weeks 6561 and 7874).	(weeks 61 and 74).		

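### SAP 11.2: maximum estradiol per 30-day period is expected to rise at day 91 through visit frequency alone (minor, descriptive)

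*SAP*

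**What the plan says.** SAP 11.2 gives one rule for E2, for all women and all periods: "Mean and maximum E2 concentrations in each 30day follow-up period will be summarized across subjects using means, medians, and SD". It also plans individual progesterone and E2 plots. Protocol 3.4 calls E2 a supporting pharmacodynamic measure, and Protocol 6.2 has it "measured every time progesterone is measured".

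The current schedule (Protocol Table 1, footnote e, in Section 3.14) is day 0, "then at day 7 and then weekly through week 32, regardless of ovulation status". The summary of changes shows what applied before Amendment 04. Under Amendment 02, samples were to be "collected at weeks 1, 2, 4, 6, 8, 10, and 12; then weekly through week 52". Two rules could add draws to that:

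- An E2 rule, deleted by Amendment 04, required weekly sampling "If the estradiol level is at or greater than 75 pg/mL during weeks 2 to 12 or weeks 52 to 78".
- A progesterone rule said "subjects with initial serum progesterone ≥3.0 ng/mL will be asked to return within 5 days for repeated progesterone measurement". A similar repeat applied at 4.7 ng/mL.

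The Amendment History dates enrolment: "27 March 2017 6 subjects have been enrolled to date", and 12 by 09 August 2017. SAP Section 2 has the undiluted cohort (1A) enrolled first. SAP Section 13 does not mention the change in E2 schedule.

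The amendment log is used here only to establish which schedule was in force when. The change itself is not an error.

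**The concern.** A maximum over more draws is larger on average than a maximum over fewer, with no change in the underlying process. If sampling roughly doubles in density at week 12, a table of the maximum by 30-day period will tend to step up at that point. Read at face value, this looks like ovarian activity returning after month 3, inside the 6-month interval the product is meant to cover. Part 2 was not run (SAP 1.1.1 footnote and 13.3), so Part 1 supplies all the E2 data. With six women per cohort, a reader who does not see draw counts cannot separate this step from a real change.

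**Working it through.** **Which schedule applied**

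- Cohort 1A: six women enrolled by 27 March 2017. Latest week 12 = 27 March + 84 days = 19 June 2017, about seven weeks before Amendment 04. All of 1A therefore passed weeks 2–12 under the earlier schedule.
- Cohort 1B: enrolled between 27 March and 09 August 2017. A woman injected by 17 May 2017 (09 August − 84 days) finished week 12 before Amendment 04. One injected on 09 August reached week 12 on 01 November 2017. Injection dates are not given, so 1B may be all on the earlier schedule or mixed. Protocol 10.1.1 also bars applying an amendment before approval.

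**Check against the plan's own count**

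Protocol Table 2 gives up to 48 post-injection progesterone/E2 samples if ovulation occurs by week 52.

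- Earlier schedule: 7 (weeks 1, 2, 4, 6, 8, 10, 12) + 40 (weeks 13–52) = 47, or 48 with a final-visit draw. This fits.
- Weekly from week 1: 52, or 53. This does not fit.

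Table 2 thus independently reflects the earlier schedule.

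**Scheduled draws per 30-day period**

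Periods are counted from injection, baseline draw excluded. SAP 8.5 defines that origin only for the Part 2 diaries, so it is assumed here.

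| Days | 1–30 | 31–60 | 61–90 | 91–120 | 121–150 | 151–180 | 181–210 |
|---|---|---|---|---|---|---|---|
| Earlier schedule | 3 | 2 | 2 | 5 | 4 | 4 | 5 |
| Weekly schedule | 4 | 4 | 4 | 5 | 4 | 4 | 5 |

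Days 91–120 hold five weekly visits (days 91, 98, 105, 112, 119).

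**Size with flat E2**

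The documents give no E2 level or variability, so all inputs below are assumptions. E2 is lognormal and constant in distribution, with AR(1) weekly correlation. A woman whose drawn E2 reaches 75 pg/mL in weeks 2–12 moves to weekly draws from the next week through week 12. Progesterone repeats are not modelled. The quantity is (mean maximum, days 91–120) / (mean maximum, days 61–90) − 1.

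Examples with one quarter of the log-variance placed between women:

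| Median (pg/mL), CV, autocorrelation | Earlier schedule with trigger | Rise | Weekly schedule | Rise |
|---|---|---|---|---|
| 30, 0.8, 0 | 56.8 → 70.9 | 25% | 65.8 → 70.9 | 8% |
| 30, 0.5, 0 | 42.0 → 51.5 | 23% | 48.9 → 51.5 | 5% |
| 50, 0.8, 0 | 103.5 → 117.9 | 14% | 109.7 → 117.9 | 7% |
| 30, 0.5, 0.8 | 39.0 → 43.3 | 11% | 41.7 → 43.3 | 4% |
| 50, 0.5, 0.8 | 66.9 → 72.2 | 8% | 69.1 → 72.2 | 4% |

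Across that whole set the rise is 8–25%, against 4–8% under weekly sampling. With the variability expressed as a within-woman log-SD of 0.3–0.7, median 30–50 pg/mL and autocorrelation 0–0.6, it is about 9–29%, against 4–9%. The low end is at median 50, log-SD 0.3, autocorrelation 0.6; the high end is at median 30, log-SD 0.7, independent draws. A repeat run moved these ends by less than one percentage point.

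**Period mean**

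With the trigger, at 30/0.5/0 the mean goes from 33.3 to 33.5 (+0.6%); at 30/0.8/0.8, from 38.9 to 38.2 (−1.8%). Across the set the change is about 2% or less.

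**The case against.** The strongest case against is about size and reach, and most of it stands.

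- A reader might compare 5 draws with 2 directly and infer a rise of about 31% (18–44%, independent draws, log-SD 0.5, range 0.3–0.7). That overstates it. The 75 pg/mL rule moved women with high E2, who drive the maximum, to weekly draws. Progesterone repeats added further E2 values, so extra draws were not confined to high E2. Part of the step (4–9%) comes from fitting weekly visits into 30-day periods and would occur on any weekly schedule.
- A reader might infer that E2-triggered sampling also distorts the period mean. The calculation does not support that.
- A reader might infer that the undiluted cohort will look more suppressed early on. The documents do not establish it. SAP 11.2 summarises E2 across subjects and specifies no comparison by cohort, and 1B's dates are unknown. A spurious cohort difference needs both a table by cohort and denser sampling in 1B.
- E2 is not a listed endpoint and carries no test or decision rule. The planned individual plots would let a careful reader see the sampling density.

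What does not fall is the step itself. It stayed positive, and above the weekly-sampling figure, in every scenario examined. Nothing in SAP 11.2 would alert a reader of the summary table.

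**Conclusion.** The point holds in limited form. Following SAP 11.2 as written, the maximum E2 per 30-day period is expected to rise at day 91 by about 9–29% with no change in E2, for all of Cohort 1A and possibly some or all of 1B. The figure depends on assumed E2 medians, variability and autocorrelation, and on the planned rather than the actual draws, which are not reported. It is an expectation, not a certainty in six women. The issue is minor and descriptive: the period mean, the PK endpoints and time to ovulation are unaffected.

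**What to change.** In SAP 11.2, for comparing maximum E2 across periods, use 28-day periods from injection and only the scheduled even-week visits (weeks 2, 4, 6, …). Leave out odd-week, triggered and repeat draws. Both schedules share these visits, and each 28-day period then has exactly 2 (weeks 2 and 4, 6 and 8, 10 and 12, 14 and 16, and so on). Scheduled sampling regardless of ovulation runs to week 32, so this covers 32/4 = 8 full periods.

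The 28-day length matters. Keeping 30-day periods with weeks 1, 2, 4, 6, 8, 10, 12 and then even weeks gives 3, 2, 2, 2, 2, 2, 3 draws. That removes the day-91 step but puts one of about 8–18% (3 versus 2 independent draws, log-SD 0.3–0.7) at days 181–210, just after the dosing interval.

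Keep the mean and the all-draw maximum as planned, print the number of draws per period beside them, and retain every value in the plots and listings. Record the change in SAP Section 13 as made after interim data review.

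The cost is a sentence or two in the SAP and a visit filter in the program; no new data are needed. The downside is that a maximum over 2 draws detects transient ovarian activity less well, which is why the all-draw maximum stays in the table.
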